Title	A double-blinded, prospective, randomized, controlled trial comparing dexamethasone versus ketorolac injection for the treatment of local inflammatory hand and upper extremity disorders: a pilot study		
Short Title	Ketorolac in hand and upper extremity soft tissue disorders		
Protocol Number	Pending		
Phase	Phase 3		
Methodology	Randomize, double-blind, prospective active control trial		
Study Duration	2 – 3 years		
Study Center(s)	Single-center – NYU Langone Medical Center		
Objectives	The primary objective of this study is to compare local corticosteroid hand and elbow injections to placebo or ketorolac to determine if there is an equal or better reduction of symptoms for common orthopaedic upper extremity disorders including: De Quervain's tenosynovitis, trigger fingers, and tennis elbow (lateral epicondylitis).		
Number of Subjects	Goal of 780 total subjects: • 260 subjects in each of the 3 treatment groups (De Quervain's tenosynovitis, trigger fingers and lateral epicondylitis)		
Diagnosis and Main Inclusion Criteria	Subjects 18 years or older, with any of the following diagnoses: De Quervain's tenosynovitis, trigger fingers, or lateral epicondylitis		
Study Product, Dose, Route, Regimen	Peritendonous soft tissue injection for De Quervain's tenosynovitis, trigger fingers and lateral epicondylitis: • 1 mL of ketorolac (30mg/mL) and 0.5 mL (5mg) of 1% lidocaine		
Duration of administration	Single administration, with a second injection permitted only once as subject desires due to no major clinical response at the 4 or 8-week follow-up.		
Reference therapy	Standard of care peritendonous soft tissue injection for De Quervain's tenosynovitis, trigger fingers, and lateral epicondylitis: • 1 mL of dexamethasone sodium phosphate (4mg/mL) and 0.5 mL (5mg) of 1% lidocaine		

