7.1 Sample Size Determination

The sample size as stated above was derived by a power analysis. A power analysis indicated that a total sample size of 200 patients randomized equally (1:1 randomization) to each treatment arm (i.e trigger finger, De Quervain's disease, and tennis elbow) without any blocking or stratification would provide 80% statistical power (alpha=.05, beta=0.20) to detect a 10% difference in mean DASH scores between cohorts assuming a common standard deviation of 25% (effect size = 10/25 = 0.4). To account for an estimated 30% loss to follow-up, we plan to enroll a total of 260 patients per treatment arm (i.e. trigger finger, De Quervain's disease, and tennis elbow). In total, there will be approximately 780 patients enrolled among all treatment arms, however we expect the trigger finger group to be the treatment arm that most rapidly enrolls patients.

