7.2 Statistical Methods

Statistics will be conducted by the statistician on faculty with the NYU Hospital for Joint Diseases. Primary analysis will consist of comparisons of the baseline functional scores (quickDASH and EQ5D). These scores will be analyzed and compared to subsequent scores at the various follow-ups (4-weeks, 8-weeks,

12-weeks, 6 months). In addition, changes in scores will also be analyzed between the baseline scores and the subsequent follow-ups. Statistical significance will be determined by p-values less than 0.05.

Secondary analysis will consist of physical exam findings and resolution of symptoms following injections as well as grip or pinch strength using pressure dynamometers to gage improved function following injections as well. In addition, observation of side effects will also be included in the secondary analysis.

8 Safety and Adverse Events

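### Enrolling 260 per disease does not cover the plan's own 30% loss: 182 patients remain, and power is about 76.5% rather than 80%

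*Combined protocol and SAP*

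**What the plan says.** Section 7.1 (Sample Size Determination) sets the requirement for each disease at "a total sample size of 200 patients randomized equally (1:1 randomization) to each treatment arm" and says that this number "would provide 80% statistical power (alpha=.05, beta=0.20". The target is "to detect a 10% difference in mean DASH scores between cohorts assuming a common standard deviation of 25% (effect size = 10/25 = 0.4". The next sentence turns that requirement into enrolment: "To account for an estimated 30% loss to follow-up, we plan to enroll a total of 260 patients per treatment arm". Three diseases at 260 give the planned total of about 780.

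The synopsis repeats this text under Statistical Methodology. Its Number of Subjects entry, "260 subjects in each of the 3 treatment groups", names the three diagnoses, so 260 is a count per disease and not per drug. Section 5.1.2 divides patients into two groups, dexamethasone and ketorolac, so 200 evaluable means 100 per drug within a disease. No inflation formula is given.

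**The concern.** Loss to follow-up is a fraction of the patients enrolled, so the required evaluable number has to be divided by the fraction retained. The step from 200 to 260 looks instead like 30% added to the evaluable number. That always gives too few patients, and the gap widens as the assumed loss rises.

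At stake is whether the design has the type II error of 0.20 that the protocol states. If 260 cannot absorb a 30% loss, the 80% power claim fails under the plan's own assumption, separately in trigger finger, De Quervain's tenosynovitis and lateral epicondylitis.

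**Working it through.** **Inputs.** From section 7.1: difference 10, SD 25, so d = 10/25 = 0.4; alpha 0.05; power 80%; 1:1 allocation; 200 evaluable, 30% loss and 260 enrolled per disease. Section 7.1 does not say whether the test is one- or two-sided, and section 7.2 says only "Statistical significance will be determined by p-values less than 0.05". I assume two-sided, for the reason given in step 1.

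**1. Reproduce the 200.**
- Normal approximation, n per drug = 2(z₀.₉₇₅ + z₀.₈₀)²/d² = 2(1.960 + 0.842)²/0.16 ≈ 98.1, rounded up to 99 (198 in total).
- Two-sample t-test: 99.08 per drug, rounded up to 100 (200 in total). Power at 100 per drug is 80.4%.
- A one-sided test would need 78 per drug (156 in total), which does not match.

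The 200 is correct for a two-sided test.

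**2. Reproduce the 260.**
- 200 × (1 + 0.30) = 260, which matches the plan.
- 200/(1 − 0.30) = 285.7, rounded up to 286, which does not.

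**3. Apply the stated loss to the stated enrolment.**
- 260 × 0.70 = 182 evaluable per disease, 91 per drug.
- Over three diseases: 3 × 182 = 546, against 3 × 200 = 600.
- Largest loss that still leaves 200: 1 − 200/260 = 23.1%.

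**4. Power with 91 per drug.**
- Noncentrality = d√(n/2) = 0.4 × √45.5 = 2.698, with 180 degrees of freedom.
- t-test power = 76.5%, so type II error = 23.5%. The normal approximation gives 77.0%.
- Effect detectable with 80% power: d = 0.4176, or 0.4176 × 25 = 10.4 points.

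**5. Power with 260 enrolled, by actual loss (two-sided t-test).**

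| Loss | Evaluable per disease | Power |
|---|---|---|
| 20% | 208 | 81.9% |
| 23% | 200 | 80.4% |
| 25% | 195 | 79.4% |
| 30% | 182 | 76.5% |

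**6. Check the alternative.** 286 × 0.70 = 200.2 evaluable, power 80.4%. Total enrolment is 3 × 286 = 858, which is 78 more than 780.

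**The case against.** The arithmetic is not in dispute. The case on the other side is about weight and certainty.

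- **Size.** The loss is 3.5 points of power. The SD of 25 is a round figure with no stated source, and at an SD of 23.95 the same 182 patients would give 80.0%. The title also calls the trial a pilot. This stands as a statement about size: the uncertainty in the SD matters more than this slip. It does not make the sentence correct, and the same synopsis labels the trial Phase 3 and makes a formal power claim.
- **What the 80% belongs to.** Strictly, the protocol attaches 80% to 200 patients, and the 200 × 1.3 formula is inferred. Both points are true. But the only purpose given for 260 is to absorb a 30% loss, and 260 less 30% is 182 however it was reached.
- **Which visit.** The 30% is tied to no visit. Follow-up is at 4, 8 and 12 weeks and 6 months (sections 3.4 and 7.2). If 30% is the cumulative loss by 6 months, earlier visits keep more patients. This stands: 182 is the number when the full 30% is missing at the visit analysed.
- **Patients or sites.** Sections 4.1 and 5.5 allow several sites per patient, each with its own identifier, so 260 may not be a clean count of patients. This also stands, and it makes 546 uncertain as a count of people. Correlation between sites in the same patient could lower power further, so the point does not help the plan.
- **Recovering lost patients.** Section 10.1 has drop-outs seen at their regular appointments, but section 7.2 gives no method for missing scores that would bring them back into the analysis.

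**Conclusion.** The sample-size statement is wrong as written. On the plan's own inputs, 260 enrolled per disease covers a loss of 23.1%, not 30%. If 30% are lost at the visit analysed, each disease has 182 evaluable patients, about 76.5% power for 10 points (77.0% by normal approximation), and 80% power only for differences of 10.4 points or more.

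This rests on a two-sided test, which is the reading that reproduces 200; an unadjusted comparison of two means at SD 25; one independent observation per patient; and the full 30% missing at the visit analysed. The practical effect is modest. The underlying requirement of 200 is sound, and only the step from 200 to 260 needs correcting.

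**What to change.** **Minimum change.** In section 7.1 and in the synopsis under Statistical Methodology, replace the loss sentence with wording such as: *Enrolment of 260 patients per disease leaves 200 evaluable if up to 23% are lost. If 30% are lost, 182 are evaluable and the power of an unadjusted two-sided comparison is about 76.5%.* State the visit to which the loss applies. This edits the same statement in two places and needs no extra patients. The stated power becomes slightly less favourable.

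**If the sponsor wants to keep 80% at 30% loss**, there are two routes.

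- *Enrol more.* Use 286 per disease, 858 in total, and update the Number of Subjects entry. The cost is 26 more patients per disease, 78 in all.
- *Adjust for baseline.* Make the primary analysis a comparison of follow-up quickDASH adjusted for baseline (ANCOVA), which multiplies the SD by √(1 − r²), where r is the baseline-to-follow-up correlation. The documents give no value for r, so it is an assumption. With 182 evaluable, power is 77.0% at r = 0.1, 78.2% at 0.2, 80.3% at 0.3 (SD 25 × √0.91 = 23.85) and 87.3% at 0.5. This route needs no extra patients only if r is about 0.3 or more. It also means rewriting section 7.2, which now lists comparisons of scores and of changes without naming a model. Analysing raw change scores is not a substitute: if 25 is the SD of a single score, r = 0.3 gives a change-score SD of 25 × √1.4 = 29.6 and power of about 62%.

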7.2 Statistical Methods

Statistics will be conducted by the statistician on faculty with the NYU Hospital for Joint Diseases. Primary analysis will consist of comparisons of the baseline functional scores (quickDASH and EQ5D). These scores will be analyzed and compared to subsequent scores at the various follow-ups (4-weeks, 8-weeks,

12-weeks, 6 months). In addition, changes in scores will also be analyzed between the baseline scores and the subsequent follow-ups. Statistical significance will be determined by p-values less than 0.05.

Secondary analysis will consist of physical exam findings and resolution of symptoms following injections as well as grip or pinch strength using pressure dynamometers to gage improved function following injections as well. In addition, observation of side effects will also be included in the secondary analysis.

8 Safety and Adverse Events

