3.1 General Design

This study will be a double-blinded prospective randomized controlled trial comparing the effects of dexamethasone (standard of care) and ketorolac in hand and upper extremity soft tissue disorders.

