3.4 Primary Safety Endpoints

Patients will follow-up after the first injection at 4-weeks, 8-weeks, 12-weeks, and 6 months post injection. During follow-up appointments patients in this study will be monitored based on history and physical exam for any side-effects associated with the administration of local soft tissue injections of dexamethasone or ketorolac.

Patients can withdraw from the study at any time if they wish. Patients whose symptoms do not improve and are candidates for surgery can withdraw from the study and have surgery to correct their specific pathology (secondary endpoint). Patients enrolled in the study will be counseled regarding the likelihood of

the injections working and will be given the opportunity for a second injection at 4 weeks from the time of the first injection if no significant symptoms have resolved. Ultimately it will be up to the patient whether they chose another injection or if they want to resort to a surgical intervention.

Patients who receive ketorolac by randomization as the therapeutic option will have an expected failure rate of approximately 30-50% based on clinical experience and literature review that shows the failure rate of dexamethasone (standard of care) on trigger fingers. The study population will be statistically analyzed biannually to determine if there is a significant difference in the rate of failures between the two groups, however a sizeable study population needs to be established before these conclusions can be drawn. If the rate of failure proves to be statistically significant between the ketorolac and dexamethasone group then the study will have to be ethically abandoned. This determination needs to take into consideration the pretreatment symptoms of the patient since patients who begin treatment with a severe trigger finger (quinnell score=4) have a different prognosis compared to patients who begin with a mild trigger finger (quinnell score=1).

4 Subject Selection and Withdrawal

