4.1 Inclusion Criteria

- Patients must be diagnosed with at least one of the following: trigger finger, de quervain's tenosynovitis, or tennis elbow (lateral epicondylitis)
- Subjects may be treated for multiple sites of pathology simultaneously or sequentially and up to three sites of pathology can receive an injection during an office visit
- Subjects may have a maximum total of two injections at each site of pathology during the study
- Age 18 years of age or older from all racial/ethnic types
- · Both males and females
- Study participants will not receive splinting as a therapeutic addition to their treatment.
- Study participants will include any NYU employee or students as these individuals also can get hand and upper extremity pathology. It will be specifically reiterated to them that their academic status or grades, or employment will not be affected by their decision to participate in this study. Record of the participation cannot be linked to an academic record.

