5.1.2 Treatment regimen

The proposed use of ketorolac in this study is outside of the FDA-approved indication and is the investigational agent in this study. Ketorolac will be administered as a peritendonous soft tissue injection of 1 mL of ketorolac (30mg/mL) and 0.5 mL (5mg) of 1% lidocaine.

Patients will be followed at the initial office visit, 4-weeks, 8-weeks, 12-weeks, and 6 months post injection to determine clinical response. A second injection can be given only once at each site of pathology if the patient desires due to no clinical response at the 4 or 8-week follow-up.

Patients will be divided into two groups. Group 1: 1 mL of dexamethasone sodium phosphate (4mg/mL) and 0.5 mL (5mg) of 1% lidocaine (*standard of care*). Group 2: 1 mL of ketorolac (30mg/mL) and 0.5 mL (5mg) of 1% lidocaine (*experimental group*). Patients will be followed at the initial visit, 4-weeks, 8-weeks, 12-weeks, and 6 months post injection to determine clinical response. A second injection can be given only once if the patient desires at the 4 or 8-week follow-up. These injections will be offered if the patient reports some improvement since the prior injection but still some persistent symptoms that have not completely resolved or if they had no response but would like another attempt to avoid surgery by receiving a second injection. The injection administered for the second time will correspond to the randomized group for the patient. Patients will not be compared separately if they receive one or two injections. However, with enough enrollment subgroup analysis can be performed to determine if receiving two injections significantly alters the outcome of the patient in regards to functional score improvement, surgery endpoint, or resolution of symptoms. The primary endpoint for the study would be resolution of symptoms or surgical intervention.

Patients receiving a second injection should be allowed to continue in the study. It is common practice for patients as part of the standard of care to receive multiple injections for hand and upper extremity pathology until these injections have been deemed non-therapeutic by the treating physician and surgical intervention is indicated.

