5.5 Method for Assigning Subjects to Treatment Groups

When a patient is enrolled and consented into the study a random envelope (labeled with an identification number) will be opened and in it will contain the group that the patient is randomized to: steroid or ketorolac. Envelopes are made using a randomization software that chooses one of the two drugs at random. When a patient is being enrolled in the study for an additional site of pathology, they will receive the same drug to which they were initially randomized at each site of pathology and a separate identifier number will be used to track the progress of each site.

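### Section 7.2 does not state the ketorolac-versus-dexamethasone contrast that 7.1 sizes, and the 'equal' half of the objective has no margin or confidence-interval rule

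*Combined protocol and SAP*

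**What the plan says.** The objective, in the synopsis and in section 2, is to compare corticosteroid with ketorolac injections "to determine if there is an equal or better reduction of symptoms". Section 3.1 describes a randomized trial "comparing the effects of dexamethasone (standard of care) and ketorolac". Section 5.1.2 states "Patients will be divided into two groups", and under section 5.5 the envelope holds "the group that the patient is randomized to: steroid or ketorolac". Section 7.1 asks for 200 patients per disease, allocated 1:1, "to detect a 10% difference in mean DASH scores between cohorts", with SD 25%, alpha 0.05 and 80% power. It raises this to 260 for 30% loss to follow-up.

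Section 7.2 then gives the primary analysis: "Primary analysis will consist of comparisons of the baseline functional scores (quickDASH and EQ5D). These scores will be analyzed and compared to subsequent scores" at 4, 8 and 12 weeks and 6 months. It adds changes from baseline and a p<0.05 criterion. It names no drug group, between-group test, model, deciding visit or confidence interval.

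The one explicit between-drug test is the twice-yearly failure-rate check in section 3.4, which begins "If the rate of failure proves to be statistically significant between the ketorolac and dexamethasone group" and leads to abandoning the trial. It is a stopping check on a different outcome.

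**The concern.** Read literally, 7.2 compares each patient's later scores with that patient's own baseline. Both arms may improve through either drug, natural recovery or regression to the mean, so improvement over baseline says nothing about the difference between the drugs. The stated primary analysis could be completed without answering the trial's question.

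Read generously, as a between-drug test of scores or changes, p<0.05 in favour of ketorolac would support 'better'. The other half of the objective stays open. With p<0.05 as the only criterion and no margin, the only result left to support 'equal' is a non-significant one, and that is also what an imprecise study of an inferior treatment produces. At stake is whether an off-label injection could be reported as equal to the standard of care when the data do not rule out a disadvantage as large as the one the trial was sized to detect.

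**Working it through.** **Inputs.** From 7.1: difference 10 (10% read as 10 points on the score), SD 25, alpha 0.05, power 80%, 1:1 allocation, 200 evaluable per disease, 260 enrolled, 30% loss. Taking 30% off 260 leaves 260 × 0.7 = 182. The 5-point and 7.5-point values below are assumptions that show a range; the documents do not call them important.

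**Reproducing 7.1.** Two-sample comparison, two-sided: n per drug = 2 × [(1.960 + 0.842) / (10/25)]² = 98.1, rounded up to 99, so 198 in total. The t-test version gives 99.08 per drug, or 198.2. The plan says 200. A one-sided test needs 78 per drug (156 in total) and does not match. Section 7.1 therefore sizes a two-sided test between two independent groups. Since drug is the only randomized factor, those groups are ketorolac and dexamethasone within one disease. This is not the within-patient comparison in 7.2.

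**Precision.** SE = 25 × √(4/N); half-width of the 95% CI = t(0.975, N−2) × SE.
- N = 200: SE 3.54, half-width 1.972 × 3.54 = 7.0 points.
- N = 182: SE 3.71, half-width 1.973 × 3.71 = 7.3 points.

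**How often p>0.05 when ketorolac is truly worse.** Noncentral t with noncentrality d/SE, for one score at one visit, one site per patient:

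| True disadvantage | N = 200 | N = 182 |
|---|---|---|
| 10 points (plan's difference) | 20% | 23% |
| 5 points (assumed) | 71% | 73% |

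The 20% is simply the plan's stated beta.

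**What a margin would require.** No margin is given, so these are assumed. Power for 'not worse' is the chance that the two-sided 95% CI excludes the margin, with no true difference and no baseline adjustment:

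| Margin | N = 200 | N = 182 | N for 80% |
|---|---|---|---|
| 10 | 80% | 77% | 200 |
| 7.5 | 56% | 52% | 352 |
| 5 | 29% | 27% | 788 |

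**Limits.** Section 4.1 says "Subjects may be treated for multiple sites of pathology simultaneously or sequentially", so the one-site assumption makes these figures approximate. The rates also change if several visits or scores count. If 'equal' required no significant difference at any of four visits, with a constant true difference and an assumed between-visit correlation of 0.5 to 0.8, p>0.05 throughout would occur about 3 to 8% of the time at 10 points and 42 to 53% at 5 points (N = 200). The plan does not say which visits would count.

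**The case against.** The strongest reply is that the between-drug intent is plain. The objective, design, randomization and sample size all concern ketorolac against dexamethasone, and the changes in scores in 7.2 are easily read as changes compared by drug. This stands. A reader might infer that the trial does not mean to compare the drugs; the documents do not support that. The fault is confined to 7.2 and to the missing rule for 'equal'.

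Second, nothing in the documents says that p>0.05 will be read as equality. That also stands: the plan is silent, and does not state a wrong rule. The concern is that its single criterion leaves nothing else to support that half of the objective.

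Third, the rates describe one test at one visit, whereas 7.2 lists two questionnaires and four visits, and the failure-rate stopping check in 3.4 might end some trials in which ketorolac is worse. The rates are therefore an illustration and not the plan's operating characteristics. The effect of the stopping check cannot be computed from the documents.

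Fourth, the functional score is not the only endpoint called primary. Sections 3.2, 5.1.2 and 5.4 name resolution of symptoms or surgical intervention, section 10.1 names resolution of symptoms, and 7.2 puts EQ-5D beside quickDASH. Choosing DASH/quickDASH follows 7.1 but is still a choice, and the fix must say so.

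Last, baseline adjustment is not the only valid method; an unadjusted difference or a change score compared by drug would also give the contrast. Adjustment is advised because the baseline scores are already collected and can improve precision.

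**Conclusion.** The concern holds in this form. Section 7.2 does not state the drug contrast that the trial is designed and sized for, and on either reading of 7.2 the 'equal' part of the primary objective has no decision rule. This is more than missing detail: followed as written, the primary analysis never compares the drugs.

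The size, for one score at one visit with SD 25, is an interval of about ±7 points. A true 10-point disadvantage would pass as non-significant in 20% of trials at 200 evaluable and 23% at 182; for an assumed 5 points the figures are 71% and 73%.

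Two further inferences are tempting and should not be drawn. One is that 'better' is untestable; a between-drug test at p<0.05 can support it. The other is that 200 per disease is necessarily too few for a 'not worse' claim; at an assumed 10-point margin with no true difference it gives 80% power.

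**What to change.** In 7.2, state that within each disease the primary analysis is the ketorolac-minus-dexamethasone difference in the functional score that 7.1 powers (DASH/quickDASH, named consistently), at one follow-up visit chosen in advance, adjusted for its baseline value, with a two-sided 95% CI. State that p>0.05 will not be interpreted as equality, and that 'better' requires the CI to exclude zero in favour of ketorolac. Then take one of two routes:

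- Pre-state and justify a margin, claim 'not worse' only if the CI excludes a ketorolac disadvantage of that size, and restate the power in 7.1 for that margin.
- Report the difference with its CI and remove the 'equal' claim from the objective.

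Reconcile sections 3.2, 5.1.2, 5.4, 7.2 and 10.1 on the primary endpoint. If resolution of symptoms, surgery or EQ-5D is kept as primary, write the same kind of between-drug CI rule for it, on its own scale. Because section 3.4 has the groups compared twice a year, the text should be settled before any such comparison is seen.

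The cost is text in 7.2, in 7.1 if a margin is chosen, and in the objective if 'equal' is dropped. No new data are needed. The downside is that a merely non-significant result can no longer be called 'equal', and a margin tighter than 10 points may be out of reach at the planned size.

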1.6.2 Potential benefits

This research study may change how patients are treated with simple hand/upper extremity inflammatory disorders.

2 Study Objectives

The primary objective of this study is to compare local corticosteroid hand and elbow injections to ketorolac to determine if there is an equal or better reduction of symptoms for common orthopaedic upper extremity disorders including: De Quervain's tenosynovitis, trigger fingers, and tennis elbow (lateral epicondylitis).

3 Study Design

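### Section 7.2 words the primary analysis as baseline against follow-up scores and does not state the ketorolac–dexamethasone comparison that section 2 asks about and section 7.1 is sized for

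*Combined protocol and SAP*

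**What the plan says.** Section 7.2 is the whole account of the analysis methods. It says "Primary analysis will consist of comparisons of the baseline functional scores (quickDASH and EQ5D"), that these are compared with the scores at 4, 8 and 12 weeks and 6 months, and that "changes in scores will also be analyzed between the baseline scores and the subsequent follow-ups". Significance is p below 0.05. Neither this paragraph nor the one on secondary analysis mentions ketorolac, dexamethasone, treatment groups or a test between groups.

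The rest of the document points to a comparison of drugs:

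- Section 2 sets out to "compare local corticosteroid hand and elbow injections to ketorolac to determine if there is an equal or better reduction of symptoms".
- Section 3.1 describes a randomised trial "comparing the effects of dexamethasone (standard of care) and ketorolac in hand and upper extremity soft tissue disorders".
- Section 5.1.2 says "Patients will be divided into two groups", one per drug.
- Section 7.1 gives each diagnosis 80% power at alpha 0.05, under 1:1 randomisation, "to detect a 10% difference in mean DASH scores between cohorts", with a common SD of 25.
- Section 3.4 plans a biannual check "to determine if there is a significant difference in the rate of failures between the two groups", as a ground for stopping.

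**The concern.** Every comparison that 7.2 puts into words is between time points. A patient's score at 12 weeks against the same patient's baseline mixes the drug effect with natural course, regression to the mean and the effect of having an injection at all. A significant improvement in either group, or in both together, leaves the section 2 question unanswered. Only the difference between the randomised groups answers it.

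The omission also leaves the form of that difference open. It could be a difference in follow-up scores, in change scores, or in follow-up scores adjusted for baseline. All three are unbiased under randomisation, but they differ in precision. An analyst working from 7.2 would have to choose, possibly after seeing data.

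**Working it through.** **Inputs from the documents.** Difference 10, SD 25, alpha 0.05, power 80%, 200 in total per diagnosis at 1:1, 260 enrolled per diagnosis, 30% loss (all section 7.1).

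**Assumptions.** The correlation r between baseline and follow-up scores is not given, so 0.3, 0.5 and 0.7 are used. The SD of 25 is taken to hold at baseline and follow-up, and to apply to quickDASH although 7.1 says DASH. Each patient contributes one site.

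**1. Which comparison does 7.1 size?** For two groups, n per group = 2 × (1.960 + 0.842)² × 25² / 10² = 98.1, so 99 per drug and 198 in total. The t-test version gives 99.08, so 100 per drug and 200 in total, the stated figure. One-sided alpha gives 78 per drug, 156 in total, and does not reproduce it.

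**2. Does 7.1 fit the comparison over time?** For a paired test the SD of change is 25 × √(2(1 − r)) = 29.6, 25.0 or 19.4. Detecting a mean change of 10 with 80% power then needs about 71, 52 or 32 patients. With 200 patients, power exceeds 99% throughout. So 7.1 fits the two-drug comparison and not the analysis worded in 7.2.

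**3. Evaluable patients.** 260 × 0.70 = 182 per diagnosis, or 91 per drug. The planned target is 100 per drug.

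**4. Three forms of the between-drug analysis.** True difference 10, two-sided 0.05. CI half-width = t × SD × √(2/n), with t the 97.5% point on 2n − 2 degrees of freedom. The SD is 25 for the follow-up score, 25 × √(2(1 − r)) for the change score, and 25 × √(1 − r²) = 23.8, 21.7 or 17.9 for the baseline-adjusted score.

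| Analysis, 91 per drug | r = 0.3 | r = 0.5 | r = 0.7 |
|---|---|---|---|
| Follow-up score: half-width; power | 7.3; 77% | 7.3; 77% | 7.3; 77% |
| Change score: half-width; power | 8.7; 62% | 7.3; 77% | 5.7; 93% |
| Baseline-adjusted: half-width; power | 7.0; 80% | 6.3; 87% | 5.2; 96% |

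At 100 per drug the follow-up score has 80% power, and the adjusted analysis about 84%, 90% or 98%.

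The adjusted analysis is the most precise at every r examined. The change score, the nearest to what 7.2 describes, has less power than the unadjusted follow-up score at r = 0.3.

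**The case against.** The best reply is that nobody would run this trial without comparing the drugs. Sections 2, 3.1 and 5.1.2 make the purpose plain. Section 7.1, in the same statistical plan, attaches alpha and power to a difference in mean DASH between cohorts. Section 5.1.2 adds that patients with one or two injections are not compared separately, which fits a main comparison by drug. The wording of 7.2 is also loose: a comparison of baseline scores needs a comparator, which could be the two groups, and the word *also* before the change scores would be redundant if the preceding sentences already meant within-patient change.

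This stands as far as intent goes, and it rules out two stronger readings that a reader might infer. One is that the investigators will judge the drugs by separate within-group p-values; no sentence says so. The other is that the failure-rate check in 3.4 is the only drug comparison with a test purpose. Section 7.1 gives a powered purpose for a functional score, although it says cohorts and does not name the drugs.

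Intent still does not supply the analysis. Section 7.1 refers to mean scores rather than changes, which leans towards a follow-up comparison, but it states no model and no use of baseline. Section 7.2, where this belongs, describes only comparisons over time.

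A further fair point is that the 77% arises because 260 is 200 × 1.3, which leaves 91 per drug after 30% loss. That is a separate matter. The gain from adjustment appears at 100 per drug as well, and in both cases its size depends on r.

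**Conclusion.** The point holds as a gap in specification. As worded, 7.2 tests improvement over time and does not state the between-drug comparison of functional scores. The randomised comparison is not biased and the sample size is not aimed at the wrong question.

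Stating the comparison with baseline adjustment raises power for a true 10-point difference from 77% to between 80% and 96% at 91 per drug, or from 80% to between 84% and 98% at 100 per drug. These ranges rest on assumed correlations of 0.3 to 0.7 and on the plan's SD of 25. That the comparison is missing from 7.2 rests on the text alone. The section should be amended.

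**What to change.** Add to section 7.2, in substance: *Within each diagnosis, functional scores at follow-up are compared between the randomised ketorolac and dexamethasone groups. The difference and its 95% confidence interval come from a linear model adjusted for the baseline value of the same score. Change from baseline within a drug group is descriptive.*

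The cost is a few sentences. No patient, visit or measurement is added, because 7.2 already relies on baseline quickDASH and EQ-5D. Within-group improvement ceases to be a primary result.

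This does not decide whether one visit should be primary, or the standing of EQ-5D and the pain scale, which section 3.2 lists with quickDASH under the primary endpoint. Those decisions belong to the investigators, would also change 3.2, and should be fixed before outcome data are examined by drug. A margin for equal efficacy and the handling of several sites per patient also need their own decisions.
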